## 4.0 Study Interventions / Interventional Agents

**4.1 Intervention arm:** The intervention is losartan, an angiotensin receptor blocker prepared in suspension per the package insert, administered at 50 mg PO twice daily for 10 days (patients with eGFR 30-59 mL/min/1.73 m^2 will be given 50 mg once daily) or until hospital discharge, whichever comes first. The supply of suspension is stable for 4 weeks refrigerated according to the package insert. Any unused doses will be discarded if unused by the 28 day time point.

- **Rationale for the duration of the intervention:** The average duration of mechanical ventilation caused by Covid-19 is approximately 14 days. We expect that if a benefit is observed, it will become apparent in that time frame. We have chosen to stop treatment at the time of discharge as the participant will have already demonstrated significant clinical improvement, and would introduce significant logistical limitations.
- **Rationale for the dose of treatment:** The lowest dose of losartan is 25 mg orally. The maximum clinical dose is 100 mg daily. Losartan has a half-life of 2 hours with an active metabolite E3174 of 6-9 hours. The threshold for blockade of angiotensin-II receptor is at least 20 mg per day. Twice daily dosing has been shown to potentiate angiotensin-II receptor blockade compared with once daily dosing. At this dose, extrapolated data suggests <70% inhibition of angiotensin-II receptors. At the highest maximum allowable dose (50 mg twice daily) we would anticipate >80% inhibition of angiotensin-II receptor. We believe this is necessary as these patients have significant pro inflammatory response. Recent reports indicate that patients with COVID19 have increased plasma Ang II levels and that Ang II levels correlate with COVID19 disease severity and viral load. AT1R inhibition is associated with decreased activity of STAT1 and NFkB downstream signaling as confirmed by western blot analysis. Furthermore, since our initial submission Losartan has been identified for its potential inhibitory effects on SARS-CoV2 viral life cycle based on

molecular docking analysis of the coronavirus macrodomain. We propose a dose increase to 100 mg daily (50 mg PO BID in patients without renal dysfunction). We have previously utilized this dose in previous RCTs in HIV ([name]/[name]). These studies confirmed the safety profile of Losartan with a mean systolic blood pressure (SBP) reduction of only 7 mmHg at 100 mg daily and excellent tolerability and safety profile. Our findings confirm prior reports of 6 mmHg mean SBP reduction for Losartan when doses at 100mg daily. Patients will receive intensive safety monitoring as this will be delivered in the inpatient setting with blood pressure checks multiple times per day and minimum required potassium, creatinine and GFR checks prior to enrollment, day 1, 3, and 7 (or prior to discharge). In addition, patients will have routine creatinine and potassium monitored if ordered clinically. We hypothesize significant benefit as 4 preliminary and observational reports out of China and the UK suggest significant reductions in disease severity and inflammatory profile for patients treated with ACEi or ARBS with no preliminary reports suggesting harm from ACEi or ARBS in Covid19 patients.

- We propose a dose of 50 mg twice daily, given significantly improved RAS blockade. This is a higher dose than we are proposing for study in outpatients, as patients will be carefully monitored with regular blood pressures and renal function testing. Furthermore, patients will have a higher severity of illness and are more likely to benefit from more robust blockade. Patients with moderate renal dysfunction (eGFR 30-59 mL/min/1.73 m^2) will be given 50 mg once daily given impaired renal clearance.

4.2 *Placebo arm:* The same volume of suspension prepared according to the package insert will be administered without the active ingredient. Any unused doses of placebo will be discarded if unused by the 28 day time point.

4.3 *Investigational new drug:* The study will be conducted under IND 148365.

4.4 *Timing of the intervention:* Treatment will continue for 10 days or hospital discharge.

4.5 *Duration of study participation:* The final follow-up will occur at 90 days after randomization to determine episodes of delayed hospitalization. Data analysis is expected to be completed within 1 year of enrollment of the final patient.

4.6 *Drug Handling, blinding, and randomization:*

Fairview Investigational Drug Services (IDS), part of M Health Fairview will oversee the preparation of treatment drug and placebo. Identical suspensions (#20) will be prepared in identical syringes and labeled with a deidentified study number coded by site and patient number. A site-specific randomization schema will be created (each site will undergo block randomization in variable permuted blocks by site and age strata). Given significant differences in outcome by age, patients will be randomized by age strata ( $\geq 60$ ,  $< 60$ ). Randomization allocation will be 1:1. IDS will not be blinded to patient randomization. All other members of the study, the participants, and the clinical care team will be blinded to treatment allocation.

4.7 *Provision of study drug to patients:* The local Fairview or HCMC pharmacy will dispense the patient specific supply to each patient after consent has been obtained and

a prescription has been received from an authorized prescriber. The investigational drug or placebo will be provided to the bedside nurse twice daily for the duration of study participation.

4.8 *Study unblinding:* MHealth Fairview, East bank Inpatient Pharmacy UMMC campus, will hold the blind for all subjects on study. In the event of an emergency and unblinding is necessary, study staff can contact [contact], option 1, then option 2. This information is included on each label.

4.9 *Biosafety:* N/A. The intervention is not a biohazard.

4.10 *Stem Cells:* N/A

4.11 *Fetal Tissue:* N/A

4.12 *Use of radiation:* N/A

4.13 *Use of Center for Magnetic Resonance Research:* N/A

## 5.0 Procedures Involved

5.1 *Screening:* Screening logs containing non-identifiable information (age, gender, race, ethnicity, location of presentation, and reason for exclusion) will be maintained for patients screened but not enrolled. Initial pre-screening to determine study eligibility will necessarily proceed under waiver of informed consent and waiver of HIPAA authorization through the screening of electronic medical records. In addition, sites will have an electronic dashboard of all pending and confirmed positive COVID-19 tests that can be used for real-time prescreening of patients. If the patient appears to be eligible based on pre-screening, and if acceptable to the treating physician, the patient will be approached by a study investigator or delegated study coordinator or research nurse. *For the sake of healthcare provider safety, and to minimize the spread of the virus, this visit will occur via a HIPAA compliant telemedicine consultation or phone.*

5.2 *Enrollment:* Patients or their legally authorized representative, with due consideration of vulnerable patient populations, (see section 9) will be eligible for consent by delegated members of the study team with appropriate training and experience in the conduct of human subjects research. At this visit, consents will be reviewed in detail with the subject or LAR. The subject or LAR will have the opportunity to ask questions. If the patient (or LAR) agrees to become a study participant, electronic consent will be obtained using HIPAA and rule 11 compliant electronic consent, stored and maintained in a secure RedCap server (see departmental policy on eConsent). For patients who are enrolled via a LAR, we will attempt to reconsent the patient for ongoing study participation. If they decline, previous information gathered will be utilized but no further information will be collected. If the patient is unable to be contacted prior to discharge or by phone following discharge, or they do not regain capacity to consent, the participant will continue to participate in study procedures under LAR consent.

- *Rationale for the use of telemedicine / phone consent:* We have chosen this method of consent *in order to minimize risk to research team and healthcare providers, and to decrease community spread of the disease.* We have prior experience using telemedicine and phone consent coupled with electronic consent form review for time-sensitive clinical trials of

stroke. While the rationale for eConsent is different in this case (minimization of disease spread during a pandemic), we believe it is appropriate for the disease and intervention being studied. Critically, the established safety profile of losartan, with minimal side effects of effects on blood pressure in healthy patients without an overactive renin-angiotension-aldosertone system, combined with the close telemedicine and EMR based follow-up methods proposed in this study make the risk : benefit ratio for the alteration of traditional consent process acceptable for participants, providers, and the public.

5.3 *Administration of study drug:* Study drug will be dispensed to bedside nurses twice daily for administration. Patients unable to take the suspension (due to endotracheal intubation) will have it administered via an orogastric or nasogastric tube, or G-tube. If the patient is unable to receive the study drug for respiratory distress, we will allow for +/- 3 hours from the scheduled time of drug administration. If this is not possible, the patient will not receive that dose, and this will be tracked.

5.4 *Patient follow-up:* Participants will receive remote telemedicine, phone, or in person evaluation by trained study personnel every day for the 10 days of the intervention period to monitor for the development of complications as well as day 15. In addition, electronic medical record labs and notes will be monitoring for the development of AE and SAEs. Data will be documented into a Redcap database. The coordinators will have patients complete 2 surveys at enrollment, day 4, day 10, and day 28 (both attached in supplement), if the patient can cooperate. If not, the reason for failure to complete the survey will be recorded. Surveys conducted within 1 day of the time point will be counted as qualifying and not missing. Patients will be contacted at day 28 (+/3 days) and 90 (+/- 3 days) for intermediate term outcomes. If follow-up procedures are not completed due to inability (patient unavailable or intubated), or due to loss to follow-up, these will not be counted as protocol deviations.

5.5 *Pharmacokinetics:* Patients undergoing this voluntary substudy will have up to another 9 mL of total blood drawn (30 mL total day 1 instead of 21-24 mL day 1. The remainder of the samples will be the same for the duration of the study). Blood will be processed, frozen at -80 C until shipping to [name] at the University of Nebraska for analysis.

5.6 *Table of events:*

	Screening/ Enrollment *	Study Day																
		1	2	3	4	5	6	7	8	9	10	11	12	13	14	15	16	17
ELIGIBILITY																		
Covid-19 Result confirmation	X																	
Inclusion/Exclusion	X																	
Informed Consent	X																	
PRESCREENING / RANDOMIZATION																		

## MEDICAL PROTOCOL (HRP-590)

SHORT PROTOCOL TITLE: Randomized control trial of losartan for inpatients with COVID-19

VERSION DATE:22APR2020

Additional labs (pregnancy, Cr, potassium) if applicable	X																	
Randomize subject	X																	
POST-RANDOMIZATION																		
Enrollment Day 0 CRFs	X																	
Dispense / administer study drug**		X	X	X	X	X	X	X	X	X	X	X	X	X	X	X	X	X
MINIMUM STUDY PROCEDURES (while inpatient, if applicable) #																		
Daily CRFs		X	X	X	X	X	X	X	X	X	X	X	X	X	X	X	X	X
Creatinine, Potassium\$	X\$	X\$	X	X\$	X	X	X	X\$	X	X	X	X	X	X	X	X	X	X
SOFA score assessment	X	X	X	X	X	X	X	X	X	X	X	X	X	X	X	X	X	X
Estimated P/F	X	X	X	X	X	X	X	X&	X	X	X						X	
Ordinal scale	X	X	X	X	X	X	X	X	X	X	X	X	X	X	X	X	X	X
Blood draws%		X	X		X		X		X		X		X				X	
Nasopharyngeal or oropharyngeal swabs%		X			X				X		X						X	
Adverse event assessment		X	X	X	X	X	X	X	X	X	X	X	X	X	X	X	X	X
PROMIS Survey	X			X						X							X	
Short Form 12 Health Survey	X			X						X							X	
STUDY PROCEDURES FOLLOWING DISCHARGE (if applicable)																		
Assessment of Hospitalization																	X	X
Estimated P/F&																	X	
Follow-up biospecimens (NP/OP swab + blood draw)																	@	
Electronic medical record / death index review																		X
Adverse event assessment																	X	X
PROMIS Survey				X						X							X	
Short Form 12 Health Survey				X						X							X	
OPTIONAL STUDY PROCEDURES																		
Pharmacokinetic Lab Draw***		X																

\*Within 48 hours of hospital admission or a positive test result, whichever is later,

## MEDICAL PROTOCOL (HRP-590)

SHORT PROTOCOL TITLE: Randomized control trial of losartan for inpatients with COVID-19

VERSION DATE:22APR2020

\*\*In women of child-bearing age, patients must confirm negative test with study personnel prior to beginning treatment as well as confirmation of acceptable birth control method

\*\*\* A subset of patients will opt-in to an additional pharmacokinetic substudy

\$ Record clinical potassium and creatinine. Required measurements occur pre-enrollment, day 1, day 3 (+/- 1 day), day 7 (+/- 1 day).

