- Evidence of bacterial co-infection
- Glasgow coma scale (daily, if available)
- Death (with date, if applicable)
- Study withdrawal, with date and time (if applicable)

- Final outcome follow-ups will be determined through a combination of patient report, electronic medical record review, and review of the social security death index (SSDI).
- All data will be stored in a password protected Redcap database, with customizable tiered access and an audit trail. All protected health information (PHI) will be marked with a PHI tag that will prevent export, so only deidentified data can be exported from the database. Only deidentified data with no PHI will be exported for analysis.
- Nasopharyngeal or oropharyngeal swabs (day 1,4,8,10,15); 30 patients will receive blood draws for pharmacokinetic analysis (day 1, hours 2, 4, and 6) and patients will provide blood samples for RAAS, RNASeq, flow cytometry, and cytokine assays, collected by study personnel or bedside nurse and placed in pre-packaged transport containers to be collected by biosafety-trained transporters, transported and processed to the University of Minnesota's BSL-3 laboratory noted above, and frozen at -80 C until later analysis for local sites. Blood samples will not exceed 30 mL day 1, and will equal ~21-24 mL on days 2, 4, 6, 8, 10, and 15). All

biospecimens will be labeled with a deidentified patient ID number to prevent inadvertent disclosure of PHI. Participants will be given the opportunity to contribute to an optional study using genetic material for future studies of patient-level responses to COVID-19. These samples will likewise be deidentified, but are theoretically identifiable biologic information.

- Cytokine assays will be conducted by [name]'s laboratory at the University of Minnesota
- RAAS pathway assays will be conducted at the Wake Forest Hypertension and Vascular Research Biomarker Analytical Core
- Pharmacokinetics will be conducted at [name]'s Antiviral Pharmacology Laboratory at the University of Nebraska

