# Only to be performed if patient is an inpatient. Otherwise move to Study procedures following discharge

% Nasopharyngeal swabs and blood draws should be collected if local logistical and biosafety procedures allow. Day 1 and 4 and 10 blood and days 1 and 10 NP or OP swabs are preferred if limited.

@ We will attempt to coordinate follow-up clinic visits within 1-2 weeks from hospital discharge to obtain nasopharyngeal and blood biospecimens

& Subject discharged before D7 will be sent home with a pulse oximeter to calculate P/F ratio and a phone call will be made at this time

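### The last required creatinine and potassium check falls at day 7 (+/- 1) or discharge, but dosing can run to day 10, so the final 3 (2-4) dosing days end without a required check

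*Combined protocol and SAP*

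**What the plan says.** Footnote $ to the table of events (5.6) tells sites to record clinical potassium and creatinine and then names the mandatory days: "Required measurements occur pre-enrollment, day 1, day 3 (+/- 1 day), day 7 (+/- 1 day". The dose rationale in section 4.1 agrees, describing "minimum required potassium, creatinine and GFR checks prior to enrollment, day 1, 3, and 7 (or prior to discharge". For anything beyond that it says: "In addition, patients will have routine creatinine and potassium monitored if ordered clinically". Section 1.6 likewise collects daily laboratory results for 10 days only where they are available.

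The drug is "administered at 50 mg PO twice daily for 10 days", or until discharge if that comes first; patients with eGFR 30-59 receive it once daily. Section 4.6 matches the twice-daily course: "Identical suspensions (#20) will be prepared in identical syringes".

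Research blood is already scheduled after day 7. Section 1.6 says the samples "will equal ~21-24 mL on days 2, 4, 6, 8, 10, and 15", and footnote % to table 5.6 ranks day 10 among the draws to keep when a site is constrained: "Day 1 and 4 and 10 blood and days 1 and 10 NP or OP swabs are preferred if limited". The stated purpose is not renal: "patients will provide blood samples for RAAS, RNASeq, flow cytometry, and cytokine assays". The payment paragraph of section 11 mentions a day-15 draw for renal function, where the site permits it.

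**The concern.** Renal failure, new or worsening, is one of the safety endpoints in section 3.3. Section 3.4 undertakes to follow kidney injury systematically because adverse event reports may be biased. Section 13.1 places declining renal function and electrolyte disturbance among the most severe risks of losartan, and section 4.1 uses close inpatient monitoring to support the 100 mg daily dose. Section 18.2 exempts renal events and potassium changes from adverse event reporting unless they are judged related or of uncertain relationship, or unless they lead to discontinuation.

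Against that background, one would expect the required laboratory schedule to reach the end of dosing. It does not. In the last few dosing days a rise in creatinine or potassium is found only if someone orders the test, and the rules in 18.2 for reducing or stopping the drug can respond to a laboratory change only once it has been measured. The affected group need not be small: the rationale for endpoint timing in section 3 cites an average hospital stay of 10 days. The documents do not say what share of patients will be dosed past day 7.

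**Working it through.** The plan states no figure for this gap, so there is nothing to reproduce. The check is a count of days and doses.

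**Inputs**
- Last required check: day 7, with a window from day 6 to day 8 (footnote $, table 5.6).
- Last dosing day for a patient who stays in hospital: day 10 (sections 4.1 and 4.4).
- Doses per day: 2, or 1 with eGFR 30-59 (section 4.1).
- Assumption: dosing starts on day 1 with the full number of doses each day. This gives 2 × 10 = 20 doses, in line with the 20 suspensions in section 4.6; once daily gives 1 × 10 = 10.

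**Formulas**
- Dosing days after the last required check = 10 − day of that check.
- Doses after it = doses per day × those days.

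**Results**

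| Last required check | Dosing days after it | Twice-daily doses | Once-daily doses |
|---|---|---|---|
| Day 6 | 10 − 6 = 4 | 8 of 20 (40%) | 4 of 10 (40%) |
| Day 7 | 10 − 7 = 3 | 6 of 20 (30%) | 3 of 10 (30%) |
| Day 8 | 10 − 8 = 2 | 4 of 20 (20%) | 2 of 10 (20%) |

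**Does another provision require a value in those days?**
- *Daily marks in table 5.6.* The creatinine and potassium row is marked on every inpatient day, but only screening and days 1, 3 and 7 carry the $ sign. The footnote makes those days mandatory; the other marks are for recording clinical values.
- *Daily SOFA to day 10.* Section 3.3 carries the last value forward when data are unavailable. A day-7 creatinine can therefore stand in for days 8-10, and no new test is forced.
- *Research blood on days 8 and 10.* The assays named in section 1.6 do not include creatinine or potassium, and footnote % makes collection depend on local logistics and biosafety.
- *Day-15 renal draw in section 11.* It comes after dosing, depends on the site, and is not among the required measurements in footnote $.
- *The words about discharge in section 4.1.* If they mean day 7 or discharge, whichever is earlier, nothing changes. If they mean a check before every discharge, patients leaving on days 8-10 are covered. Patients still in hospital after day 10 then have no required check at the end of dosing.

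**After the proposed change:** 10 − 10 = 0 dosing days remain uncovered, or 10 − 9 = 1 if a day-9 value is accepted.

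**The case against.** The strongest reply is that this is a deliberate minimum on top of ordinary inpatient care. Everyone dosed on days 8-10 is in hospital. Section 13.1 describes close clinical monitoring and daily adverse event assessment, available creatinine and potassium values are recorded, and so is the need for renal replacement therapy. Section 3 puts time to steady state at somewhat over 24 hours, so the day-3 and day-7 checks already sample steady-state exposure on the planned dose. The open period of 2 to 4 days is also no longer than the interval of about 4 days between the day-3 and day-7 checks, which nobody disputes.

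Most of this stands, and it makes the practical gap small. What it does not supply is a closing value. The interval from day 3 to day 7 ends in a required test; the one after day 7 does not. Kidney injury in these patients also depends on the course of the illness: section 3.4 itself names volume depletion and hypotension, so steady-state drug levels by day 3 do not settle the matter.

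A reader might infer three stronger things that the documents do not support:
- *That renal safety goes unmonitored after day 7.* It does not: clinical values are collected and adverse events are assessed to day 15.
- *That the renal comparison between arms is biased.* Clinical teams are blinded, and nothing in the documents gives a difference in test ordering or a count of missed events.
- *That the true gap is the 8 days from day 7 to the day-15 draw.* Five of those days (11-15) are off drug, and section 18.2 regards 3 days after the last dose as ample. Setting 8 days beside the on-drug interval of 4 days overstates the problem.

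**Conclusion.** The point holds as a modest gap in the safety schedule. For a patient dosed to day 10, 3 (2-4) dosing days follow the last required creatinine and potassium check, and none is required when dosing ends. This rests on dosing from day 1 to day 10 and on reading section 4.1 as day 7 or discharge, whichever is earlier. On the other reading, the gap is confined to patients still in hospital after day 10. Footnote $ does not mention discharge at all, so the two places should be aligned in any case.

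These are counts of days and doses, not of missed events. Most affected inpatients will probably have clinical values, though the plan does not guarantee it. The change is worth making because it is cheap and brings the schedule into line with the aim in section 3.4. The validity of the trial does not depend on it. It may be tempting also to set a day-15 counting window for the renal endpoint. That is a separate question of endpoint definition, and it would extend counting into days with no guaranteed test.

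**What to change.** In footnote $ and in section 4.1, add a required creatinine and potassium at day 10, or at last dose or discharge if either comes first. State that a clinical value from that day satisfies the requirement. Otherwise, take a routine chemistry tube with the day-10 blood that section 1.6 already schedules and footnote % already prefers. Use the same wording in both places, which also settles what section 4.1 means about discharge.

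Optionally, name the day-15 renal function draw from section 11 in table 5.6, still subject to site permission.

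The cost is one footnote edit and one sentence in section 4.1, plus one routine chemistry sample for each patient without a clinical value on the closing day. Sites that cannot perform the research draw would need a clinical draw instead. The optional day-15 entry adds no new procedure. For discharged patients it means a return visit with staff contact, so it should stay conditional, and some values will be missing.
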